There is a significant amount of research studying the role of cannabinoids in chronic pain management, however very little research has been done on post-operative pain management with cannabinoids.⁶ Specifically within urology, cannabinoids have been shown to be effective in chronic pelvic pain syndrome/chronic prostatitis and help bladder dysfunction in multiple sclerosis patients.^{7,8} Cannabinoid receptors (CB1 and CB2) are present in the bladder, testis, prostate, and vas deferens.⁹ Endogenous cannabinoids interaction with these receptors is involved in the regulation of smooth muscle contractility.⁹ Alpha-receptor antagonists have been found to decrease ureteral stent discomfort by decreasing smooth muscle contractility in the ureter.¹⁰ Theoretically, agonized cannabinoid receptors, if also present in the ureter, as they are in a significant portion of the urinary tract, could also decrease smooth muscle contractility and decrease stent related discomfort. Preclinical data have shown promise for the use in chronic pain with anti-inflammatory, antinociceptive and in the treatment of addiction⁵. There is a gap in the literature to date regarding the use of CBD oil in post-ureteroscopy pain management, and post-surgery in general, but with increasing criticism on opioid prescribing practice, it is an arena that warrants investigation. Therefore, we propose a novel double blind randomized controlled study to compare pain control and safety with CBD oil and oxycodone (opioid) in the post-operative setting after ureteroscopy for urinary calculi.

Study Design and Methods

Methods: Describe in lay terms, completely detailing the research activities that will be conducted by Mayo Clinic staff under this protocol.

This study is designed as a prospective, placebo-controlled, double blind randomized controlled trial. In a blinded fashion, half of the patients will receive the trial drug and half (the control group) will receive the placebo. Both groups will also receive a script for a rescue medication, a commonly used opioid.

The medicinal products will be packaged, and labeled so as to be unidentifiable by the patient. The patient will receive the trial drug or a placebo. Packaging will consist of a syringe labeled with the dosing and administration schedule for both drugs. Drug safety sheets will be provided as part of the package.

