Patients will be randomized to one of two groups – trial medication or placebo. Randomization schedule will be generated by the study statistician. Block randomization will be used to ensure temporal balance. Once patients have consented to being included in the study, they will be assigned a sequential study number, which will be passed onto the pharmacy study contact at the appropriate site to assign randomization allocation. They will then dispense encapsulated trial medication based on that allocation.

Blinding

This is designed to be a double blinded, placebo controlled trial in which neither the patient nor the clinical team is aware of the group allocation. The medications will be packaged inside a syringe. The medication will be dispensed to the patient with a label that describes both medications, strengths, and administration schedule. The clinical team will be blinded to the allocation and will only receive the dispensed drug from the pharmacy contact and then bring it to the discharging nurse in the recovery room for inclusion with other discharge material.

Preoperative and perioperative procedures

- Patient will undergo standard preoperative procedures including baseline blood work (CBC, BMP, and LFTs), imaging, and medical clearance as required.
- The procedure itself will be performed per standard practice of the surgeon, including choice of instruments, manner of fragmentation, and postoperative management of patient with regards to follow up appointments, stent placement and removal.

Postoperative procedures

- The study pharmacy will disguise the appropriate drug into an unlabeled generic container and dispense the prescription with appropriate instructions.
- In the recovery room, the patient will fill out a 100mm pain visual analog scale sheet which will be kept in the study drawer in the urology department.
- The patient will then be given a packet of materials for data collection along with the syringe with the blinded medication with full administration instructions and safety leaflet.
- The patient will fill out the data sheets for pain scale, trial, rescue and other medication usage, and adverse events on a daily basis for three days. The patient will also fill out the Ureteric Stent Symptoms Questionnaire (USSQ) on postoperative days 1 and 3.
- Patient will then mail the data sheets to the urology department using a provided stamped-addressed envelope or hand in the data sheets at their postoperative appointment.

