The primary outcome measure will be the pain score given by patients on the 100mm continuous visual analog scale (VAS). The VAS is an easy to use instrument for evaluating pain severity. It provides reproducible results that do not differ with age, gender or cause of pain. It is sensitive to treatment effects and data derived from it can be analyzed with standard parametric statistical techniques. Each day, patients will record their maximum and average pain scores. Surveys to record the pain scores and rescue drug (oxycodone) administration will be handed to the patient on day of surgery as well as emailed out via an external REDCap database. We will combine the results from each study and compare the primary outcome between the two groups (i.e. control group and CBD oil group) in two ways: 1. overall, and 2. on a per day basis. Secondary outcomes

- We will compare the number of use, the cumulative and per day usage of analgesic opioid medication between the two groups.
- Usage of other medications, either self-administered, or prescribed will be compared
- The rate of adverse clinical events defined as the rate of adverse drug reactions, rate of unscheduled phone calls, emergency room visits, hospital admissions, and clinic visits will be compared between the two groups. Collection of adverse events will be done by a combination of patient self-report on data sheets and data gathering from electronic medical record to search for evidence of phone calls, emergency room visits, hospital admissions, clinic visit notes.
- Comparison of ureteral stent symptom questionnaire (USSQ) scores on postoperative days 1 and 3.

Subject Information

Target accrual is the proposed total number of subjects to be included in this study at Mayo Clinic. A "Subject" may include medical records, images, or specimens generated at Mayo Clinic and/or received from external sources.

Target accrual: 90

Subject population (children, adults, groups): Adults treated at Mayo Clinic, Arizona for kidney stones with ureteroscopy.

Inclusion Criteria:

- Patients who are diagnosed with kidney or ureteral stones confirmed on imaging (CT of the abdomen and pelvis) and who elect for definitive treatment via ureteroscopy at two sites within a tertiary care institution
- Age 18-75
- Patients of either gender
- Patients of all ethnic backgrounds
- Capable of giving informed consent
- Capable and willing to fulfill the requirements of the study

Exclusion Criteria:

- History of chronic pain

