Previous work looked at pain scores after ureteroscopy for upper urinary tract calculi.^{10,11} From these, and an ongoing study at the Cleveland Clinic, we estimated the mean Visual Analog Scale (VAS) score in the control group when the rescue medication is used to be 3.5 with a standard deviation of 2.5. We assume patient in the experiment group (CBD oil) will have a lower pain score and the placebo group has at least 40% higher pain score before use of the rescue medication. We assume alpha (Type I error) equals to 0.05, power (1 - Type II error) 0.80 and the standard deviation of the pain score is 2.5 for each group. Using two-sided t-test, the sample size estimations under different scenarios are listed in the table below. At Mayo Clinic Arizona we perform over 700 surgical cases for stone disease each year, so patient accrual should be amenable to completion in 12 months.

Pain score in	Pain score in	Effect size	Required sample	Total sample size
treatment group	placebo group	(difference/SD)	size for each group	
2.0	3.5	0.6	45	90
2.25	3.5	0.5	64	128
2.5	3.5	0.4	100	200
2.75	3.5	0.3	176	352

Data Analysis Plan:

All the study data will be summarized by descriptive statistics. We anticipate the baseline characteristics between study groups will be comparable due to randomization. The point estimate and 95% confidence interval (CI) of the primary and secondary outcomes (pain score and USSQ scores) will be reported and compared by the two-sample t-test. If there is imbalance in the baseline characteristics between groups, we will fit a regression model to adjust for the possible confounding effect. The use of analgesic opioid medication (number of use, cumulative and per day usage) will be reported and compared by the two-sample t-test or Chi-square test. All the adverse events observed during the study period will be reported and summarized by frequency count and percentages.

References

- 3. https://www.cdc.gov/drugoverdose/data/index.html. Accessed December 17, 2019.
- 4. Nickel JC, Medical marijuana for urologic chronic pelvic pain. Can Urol Assoc J 2018;12(6Suppl3).

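### Two sites, but the plan does not say whether the block schedule is stratified by site, and the analysis does not name site: a cheap improvement of low severity

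*Combined protocol and SAP*

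**What the plan says.** **Sites.** The Inclusion Criteria take patients "who elect for definitive treatment via ureteroscopy at two sites within a tertiary care institution". The share expected at each site is not given.

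**Allocation.** Under Randomization and allocation, the study statistician generates the schedule and "Block randomization will be used to ensure temporal balance". After consent the patient receives a sequential number, "which will be passed onto the pharmacy study contact at the appropriate site to assign randomization allocation". The section gives no block size and no stratification factor. It does not say whether the list and the numbering run across the trial or within each site.

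**Ratio and size.** Under Methods, "half of the patients will receive the trial drug and half (the control group) will receive the placebo". Target accrual is 90, which is 45 per arm.

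**Analysis.** The Data Analysis Plan compares pain scores by a two-sample t-test. A regression model follows only if baseline characteristics turn out imbalanced. No covariate is named, and site appears nowhere in the analysis.

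**The concern.** With two centres and two dispensing points, one expects the plan to say how the list relates to site and whether the analysis accounts for it. This plan does neither.

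Site could plausibly matter. Preoperative and perioperative procedures leave instruments, fragmentation, stent placement and removal, and follow-up to the surgeon. The Rescue medication protocol leaves adjunct stent medication to the clinical team and itself names the stent as an important source of pain. If these habits differ between sites, mean pain may differ too. An arm with more patients from the more painful site would then look worse for a reason unrelated to treatment. The planned power has almost no reserve, so any avoidable noise has some cost.

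**Working it through.** **1. Reproduce the plan's sample size.** The Power Statement gives "alpha (Type I error) equals to 0.05, power (1 - Type II error) 0.80", "Using two-sided t-test", and "the standard deviation of the pain score is 2.5 for each group". The control mean is estimated "to be 3.5 with a standard deviation of 2.5". The table row for 90 patients has a treatment mean of 2.0.
- Difference 3.5 − 2.0 = 1.5; effect size 1.5/2.5 = 0.6.
- The noncentral-t solution is 44.59, so 45 per arm and 90 in total, as stated. Power at 45 per arm is 0.804.
- The other rows also reproduce (64, 100 and 176 per arm). The sample size is not in question here.

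**2. What the documents do not give.** Block size, site share and the site gap in mean pain are absent, so they are assumed: blocks of 4 or 6, 20% to 50% of patients at one site, and a gap of 0 to 2 points on the Power Statement's scale. The SD of 2.5 is taken as the SD within a site.

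**3. Imbalance within a site under one shared list.** With the trial-wide arms equal and site independent of position on the list, the arm difference at a site with share p has variance close to 90·p·(1 − p). The closed form uses a normal approximation with continuity correction, P(|D| ≥ 6) = 2·[1 − Φ(5.5/SD)]. The simulation used 20,000 schedules per setting.

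| Share p | SD of D | P(\|D\| ≥ 6), closed form | Simulated, blocks of 4 / 6 |
|---|---|---|---|
| 0.5 | √22.5 = 4.74 | 0.246 | 0.248 / 0.248 |
| 0.3 | √18.9 = 4.35 | 0.206 | 0.207 / 0.206 |
| 0.2 | √14.4 = 3.79 | 0.147 | 0.144 / 0.144 |

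The assumed block size hardly matters. With one list per site, the difference at a site cannot exceed half a block: 2 patients for blocks of 4, 3 for blocks of 6.

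**4. What such an imbalance does.** Six extra patients from one site in one arm change that arm's site share, relative to the other, by 6/45 = 0.13. This moves the treatment difference by 0.13 points per 1-point site gap. The simulated 95th percentile of the shift at a 1-point gap is 0.16 to 0.20. The planned difference is 1.5, and the standard error is 2.5·√(2/45) = 0.53. The shifts are therefore about 0.13/0.53 = 0.25 to 0.20/0.53 = 0.38 of a standard error.

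**5. Power and type I error, p = 0.3.** An unadjusted test sees total variance 2.5² + g²·0.3·0.7 for a site gap g.
- g = 1: 6.25 + 0.21 = 6.46; SE = √6.46·√(2/45) = 0.536; 1.5/0.536 = 2.80; power ≈ Φ(2.80 − 1.99) = 0.79.
- g = 2: 6.25 + 0.84 = 7.09; SE = 0.561; 1.5/0.561 = 2.67; power ≈ Φ(2.67 − 1.99) = 0.75.
- Site in the model: SE stays at 0.527; 1.5/0.527 = 2.85; power 0.80 at any gap.

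Simulation (8,000 trials per setting, blocks of 4):

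| Site gap | Shared list, unadjusted: type I / power | Site lists, unadjusted: type I / power | Site lists, site in model: type I / power |
|---|---|---|---|
| 0 | 0.052 / 0.80 | 0.051 / 0.81 | 0.052 / 0.81 |
| 1 | 0.047 / 0.79 | 0.049 / 0.79 | 0.055 / 0.80 |
| 2 | 0.046 / 0.76 | 0.036 / 0.77 | 0.048 / 0.81 |

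The 0.036 has a simple cause. Site lists remove the site contribution from the true variance, but the unadjusted test still counts it, so its effective critical value is 1.987·√(7.09/6.25) = 2.12, which gives a type I error of about 0.037.

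**The case against.** The strongest reply is that this is a gap in description and not a design error. Most of it stands.

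- **A shared list is an inference.** A reader might infer from the singular schedule and the sequential number that one list and one number sequence serve both sites, and hence that the blocks fail to balance arms within a site. The text does not say so. Routing each number to the pharmacy at the patient's site fits site-specific lists equally well, and those would balance the arms within site.
- **Numbers out of order.** One might also infer that two pharmacies drawing on one sequence could issue numbers out of order. The protocol assigns the number after consent, before it reaches the pharmacy, which only attaches the allocation.
- **Temporal balance.** One might say that the stated aim of blocking is defeated. It is not: even a shared list balances the arms over time across the trial, which is the comparison analysed.
- **Evidence that sites differ is thin.** The cited discretion is the surgeon's, and nothing says that surgeons or habits differ by site. Both sites belong to one institution, and the opioid script is the same for every patient.
- **Partial safeguard.** The conditional regression could take in site as a baseline characteristic.

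Two things survive. Either list structure leaves something to settle: under a shared list, balance within site is left to chance; under site lists, the planned test ignores the stratification. And adjustment triggered by observed imbalance, with no covariate named, does not prespecify a site term.

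**Conclusion.** The point holds as a cheap improvement of low severity. The plan enrols at two sites, does not state how the schedule relates to site, and does not name site in the analysis.

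A blocked schedule with a t-test remains valid at 90 patients. Under a shared list the simulated type I error is 0.046 to 0.052, so the documents do not support calling the test invalid. What is at stake is chance imbalance by site (roughly a 15% to 25% chance of 6 or more patients) and some precision: about 1 percentage point of power at a 1-point site gap, and 4 to 5 points at a 2-point gap (0.76 against 0.81). A 2-point gap would exceed the treatment difference sought, and nothing in the documents suggests one.

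These sizes rest on the assumed site share, block size and gap, and on reading the SD of 2.5 as within-site. If that SD already includes site variation, the same point appears as precision not gained instead of power lost.

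**What to change.** 1. **Randomization and allocation:** state that the statistician generates one permuted-block list per site, that study numbers carry a site prefix, and that each list is held by that site's pharmacy contact.
2. **Data Analysis Plan:** prespecify site as a fixed term in the primary pain model and account for it in the opioid-use comparison (a site term in the linear model, or a site-stratified test where a Chi-square test is now planned). This replaces adjustment for site only if imbalance is seen.

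**Cost:** one extra list and one residual degree of freedom (87 instead of 88), with no added patients or procedures. Two lists can each end mid-block, so the trial-wide arm difference can reach a full block (4 with blocks of 4) instead of half a block, which is negligible at 90. The list can be set only before enrolment. If a shared list is already in use, keep it, document it, and add the site term before unblinding.

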The study will use data that have been collected under another IRB protocol. Include in the Methods section and enter the IRB number from which the research material will be obtained. *When appropriate, note when subjects have provided consent for future use of their data and/or specimens as described in this protocol.*

Enter one IRB number per line, add more lines as needed

Data	Specimens Data & Specimens	
Data	Specimens Data & Specimens	
Data	Specimens Data & Specimens	

Data Analysis

Power analyses may not be appropriate if this is a feasibility or pilot study, but end-point analysis plans are always appropriate even if only exploratory. Provide all information requested below, or provide justification if not including all of the information.

Endpoints

Primary: The primary outcome measure will be the pain score given by patients on the 100mm continuous visual analog scale (VAS).

Secondary:

- We will compare the number of use, the cumulative and per day usage of analgesic opioid medication between the two groups.
- Usage of other medications, either self-administered, or prescribed will be compared
- The rate of adverse clinical events defined as the rate of adverse drug reactions, rate of unscheduled phone calls, emergency room visits, hospital admissions, and clinic visits will be compared between the two groups. Collection of adverse events will be done by a combination of patient self-report on data sheets and data gathering from electronic medical record to search for evidence of phone calls, emergency room visits, hospital admissions, clinic visit notes.
- Comparison of ureteral stent symptom questionnaire (USSQ) scores on postoperative days 1 and 3.

Power Statement:

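### The primary pain comparison is not defined: 4 to 8 unranked t-tests fit the plan's wording, all under one alpha of 0.05

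*Combined protocol and SAP*

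**What the plan says.** - **Outcome measures**, and again **Endpoints** under Data Analysis: "The primary outcome measure will be the pain score given by patients on the 100mm continuous visual analog scale (VAS"). Neither place gives a time point, a summary or a type of score.
- **Outcome measures**: "Each day, patients will record their maximum and average pain scores". **Postoperative procedures** has the diary completed "on a daily basis for three days".
- **Outcome measures** then compares the primary outcome between groups "in two ways: 1. overall, and 2. on a per day basis". This sentence comes before the list of secondary outcomes, so the daily comparisons belong to the primary outcome as written.
- **Data Analysis Plan**: pain scores are compared by two-sample t-test, with a regression model added if baseline characteristics turn out to be imbalanced.
- **Power Statement**: "We assume alpha (Type I error) equals to 0.05", two-sided, power 0.80, SD 2.5 per group. The control value is described as the "score in the control group when the rescue medication is used to be 3.5".
- **Postoperative procedures** also includes one earlier VAS: "In the recovery room, the patient will fill out a 100mm pain visual analog scale sheet". The next step reads: "The patient will then be given a packet of materials for data collection along with the syringe with the blinded medication". The role of this earlier score in the analysis is not stated.

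**The concern.** Three choices that fix the primary result are left open: which score (maximum or average), which summary (overall or a given day), and which comparison counts if they disagree. *Overall* is not defined as one value per patient. It could be a three-day mean, a three-day peak, or all patient-days pooled, and a t-test on pooled days would treat repeated scores from one patient as independent.

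The power statement does not settle the matter. Its control value of 3.5 is tied to use of rescue medication, which corresponds to neither daily score nor to a three-day summary.

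Two things are at stake. If a significant result on any of these comparisons may be presented as the primary finding, the 5% error rate is not delivered. And nobody can say which comparison the 90 patients are powered for.

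**Working it through.** **1. The plan's own sample size.** Inputs from the Power Statement: means 2.0 and 3.5, SD 2.5, two-sided alpha 0.05, power 0.80. Effect size = (3.5 − 2.0)/2.5 = 0.6. The two-sample t-test (noncentral t) needs 44.59, so 45 per group and 90 in total, as stated. The other rows also reproduce (64, 100 and 176 per group). Each row assumes one test.

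**2. Number of tests.** One score: 1 overall + 3 days = 4. Two scores: 2 × 4 = 8.

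**3. Reference values if the tests were independent.** 1 − 0.95^4 = 18.5%; 1 − 0.95^8 = 33.7%. The real tests are positively correlated, since the overall value contains the days, so the true rates are lower.

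**4. Correlated tests.** The documents give no correlations, so a range is assumed. There were 40,000 simulated null trials per setting, 45 per arm, with six normal diary scores per patient (3 days × 2 scores). The three-day mean of each score served as its overall value. All comparisons were pooled t-tests at two-sided 0.05, and success meant any one p<0.05. The last column uses the three-day mean of one score only.

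| Day-to-day / max–average correlation | 4 tests: two-sided | 4 tests: false benefit for CBD | 8 tests: two-sided | 8 tests: false benefit for CBD | One pre-specified three-day mean: two-sided |
|---|---|---|---|---|---|
| 0.3 / 0.5 | 14.4% | 7.4% | 25.1% | 12.8% | about 5% |
| 0.5 / 0.7 | 13.1% | 6.4% | 21.0% | 10.5% | about 5% |
| 0.6 / 0.8 | 12.1% | 5.9% | 18.2% | 9.0% | about 5% |
| 0.8 / 0.9 | 10.1% | 5.0% | 14.0% | 7.0% | about 5% |

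Against the nominal 2.5%, false benefit is 5.0/2.5 = 2 to 12.8/2.5 ≈ 5 times too frequent. The lower ends are not floors: at 0.9 / 0.95 the two-sided rates are about 8.5% (4 tests) and 10.9% (8 tests).

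**5. Power with a single primary comparison, 45 per group, difference 1.5 (t-test).**
- If 2.5 is the SD of the three-day mean: 80.4%.
- If 2.5 is a single-day SD, the SD of the mean is 2.5 × √((1 + 2ρ)/3), where ρ is the day-to-day correlation. At ρ = 0.3, 0.5, 0.6 and 0.8 this is 1.83, 2.04, 2.14 and 2.33. Power is 97.1%, 93.2%, 90.8% and 85.6%.

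**6. Keeping every test primary with Bonferroni, effect size 0.6.**
- 4 tests: alpha 0.05/4 = 0.0125. Power per test at 45 per group is 61.7%; 80% needs 64 per group (128 in total).
- 8 tests: alpha 0.05/8 = 0.00625. Power per test is 52.0%; 80% needs 73 per group (146 in total).

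Bonferroni is somewhat conservative here because the tests are correlated.

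**The case against.** The best defence is that the plan leans towards a single question. Aim 1 states one hypothesis of lower pain, the overall comparison is listed first, and the sample size is built on one mean difference. If overall decides and only the choice of score is open, the two-sided rate falls to 9.1%, 8.3%, 7.8% and 6.9% at the four correlation settings. If one score is also understood, it is about 5%. The phrase about a per-day basis could also mean a daily rate, as it does for opioid use, and not three separate tests.

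The inflation does depend on the success rule and on the assumed correlations, so the figures must be read as conditional. But no section states the milder reading. Numbering two ways of comparing one outcome does not rank them, and separate days are the more natural reading for a pain score. Even on the milder reading the score and the overall summary remain undefined.

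It is also fair to say that the fault could be cured with the planned t-test alone, so ANCOVA goes beyond the minimum. Two further gaps bear on the fix: there is no rule for a missing diary day, and the scale is 100 mm while the power figures are 3.5 and 2.5.

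**Conclusion.** The concern holds and must be fixed before unblinding. The plan's primary outcome admits 4 comparisons, or 8 if both scores are meant, with no ranking, no multiplicity rule and no success criterion. The sample size is arithmetically correct but belongs to a single comparison that the plan never identifies.

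The definition gap follows from the text alone. Its size, two to five times the nominal 2.5% risk of a false claim for CBD, rests on two assumptions: that any one p<0.05 would count as success, and that the correlations lie in the range shown. Every setting examined under that success rule exceeds 5% two-sided. Whatever the rule, a score or day chosen after unblinding could no longer be shown to have been pre-specified.

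**What to change.** Amend Outcome measures, Endpoints, Power Statement and Data Analysis Plan consistently, before unblinding:

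1. **Endpoint.** Name one score, for example the daily average-pain VAS. Define overall as each patient's mean over the three diary days, one value per patient, and say how that mean is formed when a day is missing.
2. **Analysis.** One ANCOVA of that mean on treatment group with the recovery-room VAS as the only covariate, two-sided alpha 0.05, reported with a 95% CI. State that the recovery-room score is taken before the first dose; the order of steps in Postoperative procedures suggests it is. If this cannot be stated, use the planned two-sample t-test on the same mean. For this comparison the specified model replaces the rule that adds regression only when imbalance is seen.
3. **Everything else.** The other score and all daily comparisons become secondary, reported as estimates with 95% CIs.
4. **Power.** State that the SD of 2.5 refers to the chosen summary, or restate it, in the same units as the VAS.

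**Cost.** Wording, and a power assumption tied to the chosen summary. The score not chosen and the single-day results can no longer carry the primary claim. No new data are needed. N can stay at 90 provided the SD of the chosen summary is no larger than 2.5 and all 90 patients supply data.

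### The withdrawal rule can remove randomised patients, no rule keeps them in follow-up or analysis, and allocation is triggered by consent, not completed surgery

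*Combined protocol and SAP*

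**What the plan says.** **Leaving the trial.** Subject withdrawal gives two ways out: the participant's own choice, and ceasing to satisfy the inclusion and exclusion criteria. The Inclusion Criteria require a patient to be able and willing to do what the study asks. The Exclusion Criteria cover being unable, for whatever reason, to meet the study's requirements, and current use of marijuana, CBD or dronabinol. Study Design and Methods also asks patients to avoid alcohol and marijuana-based products during the study.

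**Allocation.** Patients are approached at preoperative counselling in the clinic. Under Randomization and allocation, "Once patients have consented to being included in the study, they will be assigned a sequential study number", and that number goes to the site's pharmacy contact for allocation. The next sentence is "They will then dispense encapsulated trial medication based on that allocation". Under Postoperative procedures, however, "The study pharmacy will disguise the appropriate drug into an unlabeled generic container and dispense the prescription with appropriate instructions".

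**Data collection.** "In the recovery room, the patient will fill out a 100mm pain visual analog scale sheet"; the syringe is handed over after that. Daily sheets follow for three days. Patients then "mail the data sheets to the urology department using a provided stamped-addressed envelope or hand in the data sheets at their postoperative appointment". Under Outcome measures, the pain and rescue-drug surveys "will be handed to the patient on day of surgery as well as emailed out via an external REDCap database".

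**Size and analysis.** Subject Information explains that "Target accrual is the proposed total number of subjects to be included in this study at Mayo Clinic" and then gives "Target accrual: 90". The Power Statement tabulates four scenarios; the row for 2.0 versus 3.5 needs 45 per group, 90 in total. The Data Analysis Plan compares pain scores by two-sample t-test, with regression if baseline characteristics are unbalanced. It names no analysis set and no rule for missing scores, and the plan neither makes an allowance for loss nor says that none is made.

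**The concern.** The entry criteria are applied again after entry, and some of them depend on what the patient does after receiving study medication. A patient whose pain is poorly controlled might take their own CBD product; one with somnolence might stop filling in the diary. Either could be read as no longer eligible. If such patients leave follow-up or the analysis, the groups compared are no longer the groups randomised. If the reasons differ by arm, the difference in mean pain is biased, and recruiting more patients does not repair that.

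The allocation trigger creates a smaller exposure of the same kind. If the pharmacy allocates soon after consent, a patient whose operation is cancelled, or becomes bilateral (an exclusion), has already used a place in a randomisation block and possibly one of the 90. The target leaves no slack for this, since 90 is the exact requirement of the most favourable row in the power table.

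**Working it through.** **A. Passages set side by side**

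1. The withdrawal rule refers to the criteria as a whole, so they act as continuing conditions and not only at screening.
2. Some cannot change in a three-day treatment window (known allergy history, for example). At least three can: willingness and ability to do what the study asks, being unable to meet its requirements, and current cannabinoid use.
3. Each of these could be related to pain or side effects. If, for example, more placebo patients self-treated with CBD because of pain and were removed, the placebo mean would fall and the difference would shrink. Removal of CBD-arm patients for side effects could move it either way. The documents give no frequencies, so neither direction nor size can be estimated.
4. The Data Analysis Plan does not settle what happens next. An analyst who kept these patients and one who dropped them would both be following it.
5. The stated order for allocation is consent, study number, pharmacy, allocation. No step requires completed ureteroscopy or a repeat eligibility check. The postoperative listing shows when the drug is dispensed, not when the allocation is taken.

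**B. Accrual and power**

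Inputs from the Power Statement: means 2.0 and 3.5, SD 2.5, two-sided t-test, alpha 0.05, power 0.80. Arms are equal (Study Design and Methods). The standardised difference is d = (3.5 − 2.0)/2.5 = 0.6.

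Power comes from the noncentral t distribution with n1 + n2 − 2 degrees of freedom and noncentrality d × √(n1·n2/(n1 + n2)).

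Reproducing the plan: solving for 80% power gives 44.59, rounded up to 45 per group, 90 in total. The other rows (64, 100 and 176 per group) also reproduce. The arithmetic is correct, and 45 is the smallest equal-arm size that reaches 80%.

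With 90 randomised and a share L supplying no daily score, n per arm = 90(1 − L)/2. The documents give no value for L; those below are assumptions.

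| Case | n per arm | Noncentrality | Power |
|---|---|---|---|
| No loss | 45 | 0.6 × √22.5 = 2.846 | 80.4% |
| One patient lost | 45 and 44 | 0.6 × √(1980/89) = 2.830 | 79.9% |
| L = 5% | 42.75 | 0.6 × √21.375 = 2.774 | 78.3% |
| L = 10% | 40.5 | 0.6 × √20.25 = 2.700 | 76.0% |
| L = 20% | 36 | 0.6 × √18 = 2.546 | 70.9% |

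These figures hold only for the 2.0 versus 3.5 row. The plan never names a chosen row; that one is inferred from the total of 90. The Power Statement also assumes placebo pain at least 40% higher. The minimum of that range fits 2.5 versus 3.5 (3.5/2.5 = 1.4), for which the table requires 200. With 45 per arm, d = 0.4 and noncentrality 0.4 × √22.5 = 1.897, power is 46.7%.

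**The case against.** The strongest reply is that the bias is a possibility and not a stated exclusion. The withdrawal section does not say that data are dropped, the criterion on meeting study requirements sits beside inability to consent and reads naturally as a screening item, and blinding makes differential removal less likely. Most of this stands. A reader might infer that the plan discards these patients' data; the documents do not say so. The screening reading, however, is weakened by the withdrawal rule itself, which carries the criteria forward past entry.

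A reader might also infer that patients are allocated before surgery. The text does not establish that, because pharmacy preparation and dispensing are listed postoperatively. It supports asking when allocation happens. Placing it after surgery is a recommendation with an operational price, and not the correction of an error.

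On power, one missing patient costs half a percentage point and would change no decision. The diary lasts three days, and there are mail, hand-in and emailed routes, so loss may well be small. A reader might infer that the trial is underpowered through attrition, or that non-adherence dilutes the effect by a known amount. The documents give no loss rate, no adherence rate, and no statement that the assumed difference depends on full adherence, so neither inference is supported. One qualification goes the other way: counting a patient as lost only when every daily score is missing understates the loss to the per-day comparisons.

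**Conclusion.** The concern holds as a gap in protection for the randomised comparison. As written, the plan can take randomised patients off the trial for events after allocation and contains nothing that keeps them in collection or analysis. The resulting bias is possible, not shown, and cannot be sized from the documents. The allocation trigger is stated as consent, without a surgery or eligibility condition, and its actual time is ambiguous.

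The accrual part is minor. The sample-size arithmetic is right; 90 is simply the no-loss size for one row, and its power falls by about 2, 4 and 9 percentage points at assumed losses of 5%, 10% and 20%. That range takes the 1.5-point difference as given. Whether that difference is the intended design effect is a separate, unreconciled question and matters more for power than the loss allowance does.

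**What to change.** 1. **Subject withdrawal and Data Analysis Plan.** Add: *Eligibility is judged at randomisation. Diary and survey collection continues after later ineligibility or non-adherence unless consent is withdrawn. All randomised patients with at least one daily pain score are analysed in their allocated arm, and the number with none is reported by arm.* The recovery-room sheet is not a daily score, since it is completed before the syringe is handed over. Decisions on stopping study medication stay with the existing clinical rules.

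2. **Randomization and allocation.** Add: *The pharmacy takes the next allocation only after ureteroscopy is complete and the inclusion and exclusion criteria are reconfirmed; the target of 90 counts randomised patients.* Align the meaning of target accrual in Subject Information with this.

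3. **Power Statement (minor).** Say that 90 is the no-loss size for the 2.0 versus 3.5 row (80.4% power) and that no loss allowance is made. Give 78%, 76% and 71% for 5%, 10% and 20% with no daily score, labelled as assumptions. Do not restate the 1.5-point difference as the agreed design effect until it is reconciled with the 40% assumption.

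**Cost.** No additional randomised patients are needed. The price is same-day syringe preparation at two sites while patients are in recovery, somewhat more than 90 patients consented, a less favourable power statement, and possible dilution of the effect from keeping non-adherent patients in their allocated arm.
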